### 10.2.1 Interferon Alpha-2b and/or rintatolimod Non-hematologic toxicities

Considered to be possibly, probably, or definitely related to interferon alpha-2b and rintatolimod:

- **Interferon Alpha-2b:**

For grade 3 toxicity not addressed in Table 2:

- 1st episode: dose will be held and restarted at the next study visit at a dose reduction by 75%. The dose can be re-escalated if toxicity is reduced to ≤ grade 1 or baseline.
- 2nd episode: Treatment will be discontinued.

For grade 4 toxicity

- Treatment will be discontinued

Roswell Park Protocol No.: I-659920

- **Rintatolimod:**

For grade 3 toxicity not addressed in Table 2:

- 1st episode: dose will be held and restarted at the next study visit at a dose reduction by 50%. The dose can be re-escalated if toxicity is reduced to  $\leq$  grade 1 or baseline.
- 2nd episode: Treatment will be discontinued.

For grade 4 toxicity:

- Treatment will be discontinued

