#### **10.2.2 Definition of DLT**

Treatment-related DLTs will be defined as the following events that occur between Day 1 to Day 7 that are considered possibly, probably, or definitely treatment-related:

- Grade 4 hematologic toxicity.
- Grade 3 hematologic toxicity with exception of transient leukopenia, neutropenia, lymphopenia, thrombocytopenia without bleeding, or anemia lasting 7 days or less.
- Grade 4 non-hematologic toxicities, with exception of asymptomatic increased LDH or lipase or amylase.
- Grade 3 non-hematologic toxicities with exception of nausea, vomiting, diarrhea, or flu-like symptoms that are controlled by optimal supportive management.

Distinguishing clinical manifestations of COVID-19 from treatment-related DLT can be difficult because they can overlap. Manifestations of COVID-19 present at baseline (e.g., fever, shortness of breath) that are unchanged after the study regimen is begun will not be considered DLT. Worsening of these manifestations can be due to COVID-19 or treatment-related, and unless there is a specific well defined unrelated cause, all AEs that are at least possibly related to the study regimen that meet one of the criteria for DLT based on CTCAE severity will be considered DLT.

In patients who received recent chemotherapy, radiation, and/or immunotherapy toxicities from recent chemotherapy would be known to the primary oncologist, and we would interpret AEs attributed to the study regimen with this knowledge in mind. For example, if a patient received cytotoxic chemotherapy known to cause leukopenia prior to development of COVID-19, development of leukopenia following initiation of study therapy will not be considered treatment-related, depending on the expected degree and duration of leukopenia following chemotherapy.

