### **17.4 Abnormal Laboratory Values**

Only clinically significant laboratory abnormalities that require active management will be recorded as AEs or SAEs on the CRF (e.g., abnormalities that require study drug dose modification, discontinuation of study treatment, more frequent follow-up assessments, further diagnostic investigation, etc.).

If the clinically significant laboratory abnormality is a sign of a disease or syndrome (e.g., alkaline phosphatase and bilirubin 5 x the upper limit of normal associated with cholecystitis), only the diagnosis (e.g., cholecystitis) needs to be recorded on the Adverse Event CRF.

If the clinically significant laboratory abnormality is not a sign of a disease or syndrome, the abnormality itself should be recorded as an AE or SAE on the CRF. If the laboratory abnormality can be characterized by a precise clinical term, the clinical term should be recorded as the AE or SAE. For example, an elevated blood potassium level of 7 mEq/L should be recorded as “hyperkalemia”.

Observations of the same clinically significant laboratory abnormality from visit to visit should not be repeatedly recorded as AEs or SAEs on the CRF, unless their severity, seriousness, or etiology changes.

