## 19.2 Proposed Data Analysis

### 19.2.1 Safety

#### SAFETY RUN-IN DESIGN

We will use a 3+3 dose escalation scheme in order to determine the safe dose to utilize in our efficacy analysis. The 3+3 design will consider four dose levels of IFN $\alpha$  (0, 5 MU/M $^2$ , 10 MU/M $^2$  and 20 MU/M $^2$ ) and fixed dose rintatolimod (200 mg per day) administered on Days 1 and 3.

For each cohort, the given dose level will start with three patients, with three patients added to any dose level if we observe 1 out of 3 DLTs. The patients in each cohort will be staggered, so that the first patient in each cohort will have received treatment on Days 1 and 3 before the following patient(s) are enrolled in that cohort. If 2 out of 3 to 6 subjects have a DLT we will not proceed to the next dose level.

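### The DLT definition exempts asymptomatic LDH, lipase and amylase rises at grade 4 but not at grade 3, so the milder event counts and the more severe one does not

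*Combined protocol and SAP*

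**What the plan says.** Section 10.2.2 sets the window and attribution: "Treatment-related DLTs will be defined as the following events that occur between Day 1 to Day 7" and that are at least possibly related to treatment. Four bullets follow. The two non-hematologic ones are:

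- Grade 4: "Grade 4 non-hematologic toxicities, with exception of asymptomatic increased LDH or lipase or amylase".
- Grade 3: "Grade 3 non-hematologic toxicities with exception of nausea, vomiting, diarrhea, or flu-like symptoms that are controlled by optimal supportive management".

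The section then closes off discretion. Absent a specific, well-defined unrelated cause, at least possibly related events that "meet one of the criteria for DLT based on CTCAE severity will be considered DLT".

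Section 19.2.1 uses the count. One DLT in three patients adds three more patients, and "If 2 out of 3 to 6 subjects have a DLT we will not proceed to the next dose level".

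Section 17.4 limits what enters the record: "Only clinically significant laboratory abnormalities that require active management will be recorded as AEs or SAEs on the CRF". Its examples of active management include study drug dose modification, more frequent follow-up and further diagnostic work.

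**The concern.** A DLT definition should be monotone in severity: if an event counts at one grade, the same event at a higher grade should count too. Here the order is reversed for three laboratory terms. The exception for asymptomatic LDH, lipase and amylase rises sits only in the grade 4 bullet, and the grade 3 bullet's list does not mention them.

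The hematologic pair in the same section is ordered correctly: every grade 4 event counts, and exceptions appear only at grade 3. That contrast, and the absence of any stated reason for the reversal, suggest a drafting slip.

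DLT counts decide whether a level expands, clears or stops. A misclassified event can therefore change the interferon dose carried into Phase IIa.

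**Working it through.** **1. The two bullets side by side.** Take an asymptomatic, at least possibly related LDH, lipase or amylase rise on Days 1 to 7, recorded as an adverse event.

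| Course of the rise | Bullet that applies | DLT? |
|---|---|---|
| Recorded at grade 3 | Grade 3; not in its exception list | Yes |
| Seen at grade 3, then grade 4 | Grade 3 criterion already met | Yes |
| First observed at grade 4 | Grade 4; exempt | No |

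**2. Does another section repair it?** None does. Table 2, Sections 10.2.1, 10.2.3, 17.4 and 19.2.1 contain no exemption from DLT for a grade 3 rise in these analytes. Section 10.2.3 says monitoring will focus on grade 4 or worse non-hematologic toxicity, but it does not alter the definition in 10.2.2.

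**3. Can such a rise be recorded?** Section 17.4 filters by need for management, not by grade, and dose modification counts as management. For a related grade 3 non-hematologic toxicity not addressed in Table 2, Section 10.2.1 requires a hold and then a 75% interferon reduction. If the last-resort row of Table 2 (other clinically significant events) is read as covering the rise, it also requires a hold and a 75% interferon reduction. On either route a measured grade 3 rise that is treated as a toxicity can be recorded and counted.

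**4. Effect on an escalation decision, with no assumed rate.** Suppose a level already has one other DLT, and a different patient has a recorded, related, asymptomatic lipase rise.

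- At grade 3, the count is 1 + 1 = 2, and the level does not proceed.
- First observed at grade 4, the count is 1 + 0 = 1, and the level is not stopped. With three patients treated it expands to six.

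**5. Illustration with assumed rates.** The plan states no figure to reproduce. Let p be the assumed per-patient rate of a recorded asymptomatic grade 3 rise, independent between patients, with no other DLTs. Under Section 19.2.1:

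- Expand to six = 3p(1−p)²
- Clear = (1−p)³ + 3p(1−p)² × (1−p)³
- Stop = 1 − Clear

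| p (assumed) | Expand to six | Clear | Stop |
|---|---|---|---|
| 0.01 | 0.0294 | 0.9988 | 0.0012 |
| 0.02 | 0.0576 | 0.9954 | 0.0046 |
| 0.05 | 0.1354 | 0.9734 | 0.0266 |
| 0.10 | 0.2430 | 0.9061 | 0.0939 |

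For p = 0.10: expand = 3 × 0.10 × 0.81 = 0.243; clear = 0.729 + 0.243 × 0.729 = 0.9061; stop = 0.0939. If the exception also applied at grade 3, p would be 0, and both expansion and stopping from this cause would be 0.

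**6. Illustration with other DLTs present.** Assume other DLTs occur in 10% of patients. The chance of passing a level is 0.906 if grade 3 rises are exempt. If they count and occur independently in 5% of patients, the combined rate is 1 − 0.90 × 0.95 = 0.145, and the chance falls to 0.824. At 10% the combined rate is 1 − 0.90 × 0.90 = 0.19, and the chance is 0.730.

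**The case against.** The strongest reply is that the wording slip will rarely, if ever, matter.

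- **Recording.** Section 17.4 keeps clinically insignificant laboratory changes off the record, and an asymptomatic enzyme rise will often be one. There is some circularity in saying that a dose change makes the rise recordable, since the change is required only once the rise is treated as a toxicity. This narrows the problem but does not remove it: a rise can be asymptomatic and still lead to a hold, closer follow-up or further tests.
- **Measurement.** After dosing, the Main Cohort calendar (Appendix F) names only CBC and CMP, and Section 11 says only chemistry. Amylase and lipase are named as tests only for eligibility (Section 3.1), and LDH is named in none of these places. If lipase is ordered because of symptoms, the rise is not asymptomatic. This stands as a limit on frequency. Even so, Table 2 has a pancreatitis row, Section 13.1 names pancreatic inflammation as an interferon risk, and the sponsor wrote these analytes into the DLT definition.
- **CTCAE v5.0.** Its grading is not in the documents. If an asymptomatic rise can reach both grades, the rule is inverted in practice. If asymptomatic rises stop at grade 3, the exception is empty and every such recorded rise counts. The wording needs correcting in either case, but whether the inversion can occur in a patient depends on that grading.
- **Patient safety.** Counting grade 3 rises is the cautious direction, and Sections 10.2, 10.2.1 and 19.7 stop treatment for related grade 4 toxicity whether or not it is a DLT. That protects the patient but does not correct the count.
- **Assumed rates.** The documents support none of them. Section 2.4 reports no DLTs in two earlier trials of the combination, and Section 2.1 reports no MTD in over 70 patients. Both point to the low end, although those were cancer trials without COVID-19.

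**Conclusion.** The concern holds as a minor wording error in a rule that drives dose escalation. Confidence in the reading is high, because it follows from the two bullets and from the sentence that makes any qualifying related event a DLT.

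Its practical size is small and cannot be fixed from the documents. It reaches three laboratory terms, and only when they are measured, related, asymptomatic and recorded within Days 1 to 7. At assumed grade 3 rates of 1% to 2%, the range earlier experience favors, the added chance of stopping a level is about 0.1% to 0.5%. At 5% to 10% it is 2.7% to 9.4%. These figures assume independent patients and no other DLTs.

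**What to change.** Amend the two non-hematologic bullets in Section 10.2.2 so that the rule is monotone in grade. The most direct change is to add the same exception for asymptomatic LDH, lipase and amylase rises to the grade 3 bullet and keep it at grade 4. If the clinical team wants grade 4 rises to count, move the exception from grade 4 to grade 3 instead. Check the chosen wording against the CTCAE v5.0 grading of the three terms.

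Before the next escalation decision, re-adjudicate any Main Cohort patient already assessed under the current text. Section 9 describes only a first treated patient, and reports no enzyme rise.

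The cost is one sentence in a protocol amendment and a short re-adjudication.

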#### **10.2.3 Toxicity Management**

The toxicity of high dose interferon (20 million units/m^2/d) has been established by Kirkwood et al in a number of trials. Most notable was the E1684 trial (47) where HDI (20 million units/m^2/d) was administered daily for 5 days x 4 weeks. In that trial (n=143), grade 3 toxicities were 67%, grade 4 toxicities were 9% (mainly constitutional and neurologic), and there were 2 treatment related mortalities (grade 5) due to hepatotoxicity. The proportion of Grade 3 and 4 toxicities in that trial were 48.2% for constitutional toxicities (defined as ‘worst grade of any constitutional toxicity, including fever, chills, flu-like symptoms, fatigue, malaise, and diaphoresis), and 66% for non-constitutional toxicities (23.8% for myelosuppression, 13.9% for hepatotoxicity, 28% for neurological toxicity).

Roswell Park Protocol No.: I-659920

While the combination of HDI and rintatolimod may lead to synergistic additive side effects, we will monitor subject toxicities for unexpected increases in constitutional symptoms, myelosuppression, hepatotoxicity, and neurological toxicity. We will focus on monitoring for grade 3 or greater treatment related hematologic toxicities, and grade 4 or greater treatment related non-hematologic toxicities. A non-informative prior distribution of SAEs will be utilized to develop the safety stopping rules (details in Section 19).

To our knowledge, the combination of HDI and rintatolimod has not been tested previously in patients with COVID-19. Therefore, we may observe adverse events that were not observed in trials of cancer and specific adverse events may be more severe in patients with COVID-19. One possibility is worsening of acute lung injury or systemic inflammatory response. Though the protocol does not specify specific treatments for such AEs, agents used for cytokine release syndrome, e.g. Tocilizumab, or JAK2, TNF $\alpha$ , IL-1 inhibitors, may be used, based on physician judgment.

- **Gastrointestinal Toxicity**

- Nausea and/or vomiting should be controlled with adequate antiemetic therapy. Prophylactic antiemetic therapy can be used at the discretion of the investigator/sub-investigator. Subjects are encouraged to take plenty of oral fluids.
- Diarrhea should be managed with appropriate antidiarrheal therapy. Subjects should be encouraged to take plenty of oral fluids. If symptoms do not decrease to grade 1 or less with adequate antidiarrheal therapy, all protocol drugs should be held until resolved to < grade 1.

- **Pain**

- For fever or mild local pain, acetaminophen will be used at the discretion of the investigator/sub-investigator or designee.

- **Immunogenicity risk:** Given the limited exposure to interferon alpha-2b (administered on Days 1 and 3), the risk of anti-drug-antibodies is very low. Hypersensitivity reaction can occur (described below). Our plan is to assess all AEs, including immunologic complications, and to provide appropriate management.

- **Hypersensitivity Reactions**

Caution: Subjects who had a mild to moderate hypersensitivity reaction have been successfully re-challenged, but careful attention to prophylaxis and bedside monitoring of vital signs is recommended. Hypersensitivity reactions to interferon alpha-2b and/or rintatolimod will be managed as follows:

- Mild symptoms (e.g., mild flushing, rash, pruritus): Complete infusion. Supervise at bedside. No treatment required.
- Moderate symptoms (e.g., moderate rash, flushing, mild dyspnea, chest discomfort): Stop infusion. Give intravenous diphenhydramine 25 mg and intravenous dexamethasone 10 mg. Resume infusion after recovery of symptoms at a low rate, then, if no further symptoms, at full dose rate until infusion is complete. If symptoms recur, stop infusion. The subject should receive no additional interferon alpha-2b or rintatolimod. Record toxicity.

Roswell Park Protocol No.: I-659920

- Severe life-threatening symptoms (e.g., hypotension requiring pressor therapy, angioedema, respiratory distress requiring bronchodilation therapy, generalized urticaria): Stop infusion. Give intravenous diphenhydramine and dexamethasone as above. Add epinephrine or bronchodilators if indicated. If wheezing is present, that is not responsive to bronchodilators, epinephrine is recommended. Subject should be removed from further protocol therapy. Report as serious adverse event.

### **10.3 General Concomitant Medication and Supportive Care**

There are no restrictions on general supportive care, which will be administered based on newest standards of COVID-19 care.

### **10.4 Duration of Study Treatment**

A total of 2 daily doses over a 4-day day period of treatment is planned.

The participant may stop treatment earlier than planned in the event that the following occurs:

- Unacceptable toxicity
- Progression to severe COVID-19 infection, defined by new or worse pulmonary infiltrates on Chest X-Ray or CT imaging plus one of the following: room air  $\text{SaO}_2 \leq 92\%$ , room air  $\text{PO}_2 < 70 \text{ mm Hg}$ , or  $\text{PAO}_2-\text{PaO}_2 \geq 35 \text{ mm Hg}$ , and/or requiring mechanical ventilation
- Withdrawal of consent from study
- Participant non-compliance with study requirements

## **11 PROCEDURES INVOLVED**

Informed consent **MUST** be completed prior to receiving any study related procedures.

**To limit exposure of COVID-19 to staff**, patients will be provided with a surgical mask on entry to Roswell Park. The patient will be escorted to the site of drug administration using a dedicated elevator and immediately placed in a room with the door closed. All staff in contact with patients will don PPE. Infusions will be administered in a room with a closed door. History will be obtained by trained staff by phone in advance of study-related visits. Physical exam will be limited to vitals and auscultation of lungs. Following completion of treatment, the patient will be escorted to his/her vehicle by trained staff. A specific SOP will be developed to minimize contact between study subjects and staff and patients.

### **11.1 Screening**

Within 3 days prior to treatment initiation and may be the same day as initiation of study treatment:

- Recording of concomitant medications
- Medical and Surgical History
- Physical exam (lung auscultation), Vital Signs and weight;  $\text{SaO}_2$
- ECOG Performance Status Assessment
- Hematology
- Chemistry
- Arterial blood gas

Roswell Park Protocol No.: I-659920

- Serum HCG pregnancy testing (within 3 days of Day 1 in women of child-bearing potential only)
- EKG
- Chest X-ray or CT imaging (NOTE: If a chest CT is ordered as standard of care prior to starting treatment, a chest x-ray is not required)
- Nasopharyngeal swab
- Evaluations Performed on each day of treatment [(Day 1 and Day 3 (+ 1 day)]: Recording of concomitant medications
- Recording of Adverse Events
- Targeted physical exam
  - Auscultation of lungs
  - Vital Signs (temperature, blood pressure, pulse rate and respiratory rate, SaO2) will be performed pre- treatment and at 30 and 60 minutes post rintatolimod ( $\pm$  5 minutes)
- ECOG Performance Status Assessment
- Hematology
- Chemistry
- Blood (30cc) for correlative studies: On Day 1 treatment and Day 3 treatment, prior to treatment and within 1 hour after end of infusion treatment (two draws on each of these days).
- Nasopharyngeal swabs for viral quantification by quantitative PCR

### **11.2 Follow-up Visits on Days 7 ( $\pm$ 1 day) and 14 ( $\pm$ 3 days)**

- Recording of concomitant medications
- Recording of Adverse Events
- Targeted physical exam
  - Lung auscultation and Vital Signs
- ECOG Performance Status
- Hematology
- Chemistry
- Blood (30cc) for correlative studies
- Nasopharyngeal swabs for viral quantification by quantitative PCR

### **11.3 Correlative studies (blood samples)**

Three (10 mL) green-top heparinized tubes and one red-top tube of blood will be collected via venipuncture for biomarker analysis at multiple time points (please refer to **Appendix F: Study Calendar**).

Tubes will be labeled with the participant's initials, participant's study number, clinical study number, time of collection and protocol day. Samples will be sent at room temperature to the attention of Laboratory Medicine – Protocol Clinical Research Support (pneumatic Station 19) where they will get accessioned for tracking. Once specimen receipt has been documented, the specimens will be sent at ambient temperature to pneumatic station 641 (located in CCC LOB-4th floor). The [name] Laboratory will be notified via telephone *and* e-mail (all contacts to be copied with each e-mail: see contact information below) prior to sample shipment and, the samples will

Roswell Park Protocol No.: I-659920

be held in CSPO until a response is received acknowledging that personnel are available to procure the samples from the pneumatic tube station. Samples will be processed and stored in the [name] Laboratory for future analysis.

Roswell Park Comprehensive Cancer Center  
[name] Laboratory  
[name]  
Attn: Study Number: I-659920  
[name]  
[name]  
[contact] [name], [name]  
[contact]  
[[contact]](mailto:[contact])  
[[contact]](mailto:[contact])  
[[contact]](mailto:[contact])

Preliminary analyses will include the pre- and post-treatment cytokine levels and immune cell subsets, via RT-PCR, flow cytometry assays, or alternative laboratory methods. . Cytokine measurements will involve ELISAs using validated antibodies and will include generation of a standard curve with known quantities of the analyte and use of appropriate specificity controls, as recommended by the manufacturer. For cryopreserved samples, we will test for batch effects and repeat measurements on 10% of samples over a 3-month period to rule out loss of analyte detection by cryopreservation.

Below is a general description of processing of blood that might be modified per [name] judgment. Plasma samples are to be separated from whole blood and processed at 4°C using a refrigerated centrifuge at approximately 3000 rpm for 10 minutes with the plasma (0.5 ml aliquots – as many as available) being aliquoted into cryovials per time-point. The samples will immediately be frozen at -70°C or below until analyzed. PBMCs will then be obtained by Ficoll gradient as per the lab's standard procedure. Two of the tubes will be pooled and the PBMCs will be frozen in Gibco Cell culture freezing media and will be stored in LN2 until time of analysis. The remaining tube of PBMCs will be frozen in RNA later and will be stored in -70 degrees or below until analyzed. Serum will be collected from red top tubes and 0.5 ml aliquots (as many as available) will be frozen at -70°C. The screw cap polypropylene cryogenic tubes will be labeled with the clinical study number, participant's MR number, participant's study number, protocol time point, protocol day, date and time of draw.

As a component of exploratory aims, blood will be analyzed to assess pre- and post- treatment chemokine and immune cell subsets, via ELISA, RT-PCR, and flow cytometry assays to obtain insights into the synergy between rintatolimod and individual concentrations of IFN $\alpha$ .

In the induction of known mediators of anti-coronavirus responses and factors of intracellular immunity against RNA viral infections in general, we may also evaluate the levels of expression of myxovirus resistance gene (MxA), protein Kinase R (PKR); oligoadenylate synthetase-2 (OAS2); RNase-L; IFN-stimulated gene-15 (ISG15); IFN-induced proteins with tetratricopeptide repeats (IFIT1) and IFN-inducible transmembrane protein 3 (IFITM3), as well TLR3, RIG-I, MDA5, IRF3, IRF7, in nasopharyngeal swabs material and blood cells of patients on all tiers of treatment, using RT-PCR and, potentially, intracellular protein expression (flow cytometry and image stream).

Roswell Park Protocol No.: I-659920

**Note:** All investigator or analyzing research laboratories housing research samples need to maintain current **Temperature Logs** and study-specific **Sample Tracking and Shipping Logs**. The Principal Investigator/Laboratory Manager **must** ensure that the stated lab(s) have a process in place to document the receipt/processing/storage/shipping of study-related samples/specimens. This is required for both observational and interventional clinical studies collecting clinical samples.

